## 2. STUDY OBJECTIVES AND ENDPOINTS

### 2.1 Objectives

The objectives of this study are to:

- Assess safety and tolerability of imlifidase in combination with standard IVIg treatment in GBS subjects
- Evaluate pharmacokinetics of imlifidase
- Evaluate pharmacodynamics profile of imlifidase
- Evaluate immunogenicity of imlifidase
- Evaluate efficacy of imlifidase in subjects with GBS
- Evaluate quality of life after imlifidase treatment in subjects with GBS
- Evaluate healthcare resource utilization after imlifidase treatment in subjects with GBS
- Evaluate the contribution of a dose of imlifidase on outcomes with respect to severity of symptoms and recovery time through a comparison with an externally matched cohort of GBS subjects
- Evaluate the effect of imlifidase on exploratory biomarkers

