##### 3.1.3 Assessment Procedures

The subjects will be followed clinically on Days 1-8, 15, 29, 57, 92 and 180 days after imlifidase infusion and additionally with a 360-day telephone contact to assess GBS DS, R-ODS, capture health status in a questionnaire and AEs.

After study completion, all study subjects will be followed up regularly according to clinical practice at the site in question.

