### **Visit 3 (IVIg treatment), Day 3-7**

All subjects will receive standard care IVIg infusion starting Day 3, at least 48 hours after end of the imlifidase infusion (0.4 g IVIg/kg for 5 days [total dose 2 g/kg]), see [Section 5.2.3](#) for details on infusion rate etc.

The following activities and assessments will be performed in the morning **before start of IVIg infusion:**

- Safety local laboratory (Clinical Chemistry, Haematology, and Urinalysis), Day 3
- PD and ADA, Day 3
- Exploratory biomarkers, Day 3
- GBS DS and MRC sum score Days 3, 4, 5, 6 and 7

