### 7.1 Assessments Related to Endpoints

#### 7.1.1 GBS Disability Score (GBS DS)

The GBS DS will be assessed at all visits for all subjects. GBS DS is a widely accepted and easily obtainable scoring system to assess disability status of GBS subjects.

The score is as follows:

0 = Healthy

1 = Minor symptoms and capable of running (subjects must be asked to run)

2 = Able to walk independently 10 meters or more but unable to run

3 = Able to walk more than 10 meters across an open space with help

4 = Bedridden or chair bound

5 = Needing mechanical ventilation

6 = Dead

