### 1.1 Study objectives and endpoints

#### 1.1.1 Objectives

The objectives of this study are to:

- Assess safety and tolerability of imlifidase in combination with standard IVIg treatment in GBS subjects

- Evaluate pharmacokinetics of imlifidase
- Evaluate pharmacodynamic profile of imlifidase
- Evaluate immunogenicity of imlifidase
- Evaluate efficacy of imlifidase in subjects with GBS
- Evaluate quality of life after imlifidase treatment in subjects with GBS
- Evaluate healthcare resource utilization after imlifidase treatment in subjects with GBS
- Evaluate the contribution of a dose of imlifidase on outcomes with respect to severity of symptoms and recovery time through a comparison with an externally matched cohort of GBS subjects
- Evaluate the effect of imlifidase on exploratory biomarkers.

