## 1.1.2 Endpoints

### 1.1.2.1 Efficacy

The efficacy endpoints are the following:

- GBS Disability Score (DS):
  - Proportion of subjects with improvement of one or more grades in disability outcome (on the 6-point GBS DS) over time (i.e., at all post-baseline visits)
  - Proportion of subjects with improvement of two or more grades in disability outcome (on the 6-point GBS DS) over time (i.e., at all post-baseline visits)
  - Proportion of subjects with improvement of three or more grades in disability outcome (on the 6-point GBS DS) over time (i.e., at all post-baseline visits)
  - Change in GBS DS over time (i.e., at all post-baseline visits)
  - Proportion of subjects able to walk unaided ( $GBS\ DS \leq 2$ ) over time (i.e., at all post-baseline visits)
  - Time (days) to improvement by at least one, two and three grade(s) on the GBS DS
  - Time (days) to walk independently ( $GBS\ DS \leq 2$ )
  - Proportion of subjects that reach  $GBS\ DS \leq 1$  by week 26
  - Time (days) to run ( $GBS\ DS \leq 1$ )
- Rasch-built Overall Disability Scale (R-ODS):
  - Proportion of subjects with an increase from baseline in R-ODS scale by at least 6 points on the centile metric score over time (i.e., at all post-baseline visits)
  - Proportion of subjects with all R-ODS items above 0 at week 26
- Change in MRC sum score over time (i.e., at all post-baseline visits).
- Ventilation support (GBS DS 5):

- Proportion of subjects requiring mechanical ventilation support (GBS DS 5) (i.e., at all visits)
- Time (days) on mechanical ventilation
- Time (days) in hospital and in an ICU
- Quality of life as measured by EurQol EQ-5D Health Questionnaire (EQ-5D-5L) at 4 weeks and later.

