### 2.1 Overview of study procedures

All subjects will receive imlifidase (Day 1) prior to standard of care IVIg. Disability scores to assess disability status and capture activities and social participation will be evaluated. Blood samples for safety, pharmacokinetics, and pharmacodynamics will be collected, and subjects will be closely monitored after infusion with imlifidase.

Subjects will be followed clinically on days 1-8, 15, 29, 57, 92 and 180 days after imlifidase infusion and additionally with a 360-day telephone contact to assess GBS DS, R-ODS, capture health status in a questionnaire, and AEs.

Safety parameters will be measured up to Day 180. Concomitant medication will be recorded throughout the study.

Reporting of adverse events will be done from signing of informed consent and throughout the study.

After study completion, all study subjects will be followed up regularly according to clinical practice at the site in question.

Figure 1. Overview of study

The planned tests are summarised in the **Study Flow Chart Table** outlined in the study protocol.

Note, schedule of Study Flow Chart (i.e., assessments and procedures) may change between protocol versions, please refer to corresponding schedule relevant for each protocol version.

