## 4.7 Efficacy analysis

### 4.7.1 GBS Disability Score (GBS DS)

The GBS Disability Score (GBS DS) used for the efficacy endpoints will be assessed for all subjects as per the schedule of assessments. The score is defined as follows:

0 = Healthy

1 = Minor symptoms and capable of running (subjects must be asked to run)

2 = Able to walk independently 10 meters or more but unable to run

3 = Able to walk more than 10 meters across an open space with help

4 = Bedridden or chair bound

5 = Needing mechanical ventilation

6 = Dead

Summary statistics will be presented in tables for the actual values and absolute change from baseline by time point. Also, shift tables will be presented to show the change from baseline as compared to post-baseline visits for the GBS DS.

In addition, the number and percentages of subjects with improvement of at least one, two or three grades, respectively, on the GBS DS will be presented by time point.

Similarly, the number and percentage of subjects able to walk unaided (GBS DS  $\leq 2$ ) and run (GBS DS  $\leq 1$ ), respectively, will be presented by time point.

Lastly, the following Kaplan-Meier analysis summary tables and plots will be presented:

- Time to improvement by at least one grade on the GBS DS
- Time to improvement by at least two grades on the GBS DS
- Time to improvement by at least three grades on the GBS DS
- Time to walk independently (GBS DS  $\leq 2$ )
- Time to run (GBS DS  $\leq 1$ )

Study end/discontinuation will be considered as censoring for subjects that do not have the event. In addition, the survival function will start at 0, since all these are “positive” events.

For each endpoint two separate Kaplan-Meier plots will be presented, one up to Day 29 (collected part of Visit 6) and one up to Day 360 (collected as part of Visit 10), including the subjects at risk at specific timepoints. Also censored observations will be marked as such on the plot.

The summary tables for the corresponding Kaplan-Meier analysis will include the following for specific timepoints up to Day 360: subjects at risk, number of subjects with events, censored observations, proportion estimates and associated pointwise 95% confidence interval (CI).

A separate table will present the number of subjects included in the analysis with corresponding number of events, number of censored observations and summary statistics for the time to event (minimum, maximum, median and associated 95% CI, quartiles).

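### Recovery quantiles that fall after Day 8 will be reported late and clustered on visit days, because GBS DS is then seen only at gaps of 7 to 180 days and SAP 4.7.1 plans ordinary right-censored Kaplan-Meier

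*SAP*

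**What the plan says.** SAP 1.1.2.1 defines five time-to-event endpoints in days: improvement by at least one, two and three GBS DS grades, walking independently ("Time (days) to walk independently") and running. SAP 4.7.1 analyses all five by Kaplan-Meier. Subjects without the event are censored at study end or discontinuation. One table gives proportions with pointwise 95% confidence intervals at unspecified timepoints, and another gives "summary statistics for the time to event (minimum, maximum, median and associated 95% CI, quartiles". The section has no rule for the event date, no interval-censored method and no caveat about visit spacing.

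On ascertainment, Protocol 7.1.1 says "The GBS DS will be assessed at all visits for all subjects". Subjects are "followed clinically on days 1-8, 15, 29, 57, 92 and 180 days after imlifidase infusion and additionally with a 360-day telephone contact" (SAP 2.1). In the IVIg week the Protocol lists "GBS DS and MRC sum score Days 3, 4, 5, 6 and 7", so the first week is scored daily. The visit lists in Protocol 6.1 ask for the score on the day; none asks when the subject first walked or ran since the previous visit.

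**The concern.** Kaplan-Meier with right censoring needs one exact date per event. Here the exact date is unknown. All that is known is that recovery happened after the last visit without it and by the first visit with it. If the detection visit is used as the event date, the curve estimates the time to the first scheduled visit after recovery.

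The error runs in one direction, late, and its size depends on where recovery falls in the schedule. The confidence interval for the median is built from the same visit dates. It reflects sampling variation among 30 subjects but not the weeks or months in which each recovery could have occurred. The study hypothesis includes quicker recovery (Protocol 1.3), so a median quoted in days will be read as how fast these patients recovered.

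**Working it through.** **Inputs from the documents**
- Assessment days 2 to 8, 15, 29, 57, 92, 180 and 360, with windows from Day 8 on of +2, ±2, ±3, ±4, ±4, +14 and +14 days (Protocol 6.1).
- About 30 subjects (SAP 2.2).
- 20% unable to walk at 6 months; two thirds lose unaided walking (Protocol 1.1).

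**Assumptions**
- The documents give no recovery distribution, expected median or event count, so there is no stated figure to reproduce.
- I take 20 to 30% of enrolled subjects as not walking at Day 180. The lower value applies the 20% directly. The upper is 0.20 / (2/3) = 0.30, if all those patients come from the two thirds who lost walking.
- Recovery is exponential, with Weibull shapes 0.6 to 1.3 as sensitivity. No visits are missed, events are dated at the detection visit, and time runs from dosing (study day minus 1).

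**Step 1: gaps.** 15−8 = 7, 29−15 = 14, 57−29 = 28, 92−57 = 35, 180−92 = 88, 360−180 = 180 days. With windows, the first ranges from 3 to 9 days and the last from 166 to 194. Within the daily phase the gap is 1 day, and at most 3 (Day 7 to a Day 8 visit held on Day 10).

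**Step 2: true quantiles for walking.** Let S(t) = exp(−kt) with k = −ln(p)/180, where p is the share not walking at 6 months. The q-quantile is −ln(1−q)/k.
- p = 0.20: k = 1.609/180 = 0.00894; quartiles 32, 78 and 155 days.
- p = 0.30: k = 1.204/180 = 0.00669; quartiles 43, 104 and 207 days.

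**Step 3: what a very large trial would report with visits on their nominal days.** The share recovered by each visit is 1 − exp(−kt).

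| Days since dosing | 28 | 56 | 91 | 179 | 359 |
|---|---|---|---|---|---|
| p = 0.20 | 22% | 39% | 56% | 80% | 96% |
| p = 0.30 | 17% | 31% | 46% | 70% | 91% |

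The reported quartiles are the first visits at which 25, 50 and 75% are reached: 56, 91 and 179 for p = 0.20, and 56, 179 and 359 for p = 0.30. All of them are visit days.

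**Step 4: trials of 30, by simulation with the visit windows** (averages over trials of Q1 / median / Q3, in days).

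| Not walking at 6 months | True | Kaplan-Meier at detection visit | Interval-censored, linearly interpolated |
|---|---|---|---|
| 20% | 32 / 78 / 155 | 46 / 103 / 220 | 35 / 79 / 154 |
| 30% | 43 / 104 / 207 | 61 / 147 / 306 | 46 / 112 / 220 |

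Repeat runs put the average reported medians at 103 to 106 and 147 to 149, so about 105 and 148.

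**Step 5: sensitivity to shape.** Over shapes 0.6 to 1.3 and 20 to 30% not walking, the Kaplan-Meier median is on average 17 to 54 days late; the interpolated interval-censored median is about 2 to 14 days late. Only 2 to 21% of subjects walk by Day 8 in these scenarios, and the true first quartile lies at 10 to 60 days, so all three walking quartiles fall after the daily phase.

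**Step 6: fast endpoints (exponential).** A true median of 4 days is reported on average as 4.4, and 7 as 8.6. With a true median of 7 the third quartile is still affected: true 14, reported on average 21.

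**The case against.** The best defence has four parts.

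- **The dating rule is inferred.** SAP 4.7.1 never says the detection visit is the event date. That is correct, but no other date is collected. If another rule was meant, it has to be written down.
- **Unbiased summaries are already planned.** SAP 4.7.1 gives numbers and percentages by visit, shift tables, and Kaplan-Meier proportions with pointwise intervals. With a shared schedule and no missed visits, Kaplan-Meier read at the visit days equals the Turnbull estimate, so the interval containing the median can be found by a careful reader. This stands as mitigation. It does not correct the tabulated medians, quartiles and confidence intervals in days.
- **Dating at first documentation is common, and nothing hangs on it.** No hypothesis is tested (SAP 4.1.1) and no decision rule uses these medians. The harm is to interpretation only.
- **The near-unbiased figures in Step 4 rest on linear interpolation**, which the proposed fix does not use. True: the fix reports the interval itself and claims no more.

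A reader might also infer more than the documents support:

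- *That all five endpoints mainly report the visit calendar.* Daily scoring makes quantiles reached by Day 8 nearly exact, which may cover the median for one-grade improvement. No recovery distribution is given for the other endpoints.
- *That the overstatement reaches about 80 days, or that true medians of 100 and 150 days are reported only about 8 days apart.* Those figures come from taking the median of the per-trial medians, which snaps to a visit. The average reported medians are about 144 and 208. A true exponential median of 150 days also implies 0.5^(180/150) = 44% not walking at Day 180, outside the range anchored to the Protocol.
- *That this analysis defeats the recovery-time objective.* That objective reads "outcomes with respect to severity of symptoms and recovery time through a comparison with an externally matched cohort" (SAP 1.1.1). The comparison, if feasible, has its own protocol and SAP (SAP 2), and the control cohort's visit schedule is not in these documents.

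**Conclusion.** The concern holds for quantiles that fall after Day 8. There the planned median and quartiles are biased late and cluster on visit days, and the confidence interval leaves out the gap width. For walking, anchored to the Protocol's own prognosis figure, the median is about 27 days late (78 reported as about 105) to 44 days late (104 reported as about 148) under an exponential, and 17 to 54 days late on average over the shapes tried. These sizes depend on the assumed distribution and on 20 to 30% not walking at Day 180; the late direction does not. Running and the two- and three-grade improvements were not separately calibrated. This is a worthwhile correction to how results are reported; it does not invalidate the study.

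**What to change.** In SAP 4.7.1:

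1. Define each event as the interval from the last visit without it (exclusive) to the first visit with it (inclusive). Subjects never seen with the event are right-censored at their last GBS DS assessment.
2. Add the interval-censored nonparametric (Turnbull) estimate for the five endpoints. Report the median and quartiles as the visit interval containing them, for example between Day 29 and Day 57.
3. Keep the planned Kaplan-Meier plots and tables, state that the event is dated at the detection visit, and label them *time to first visit at which improvement was recorded*. Make the scheduled visits the timepoints for the proportions with pointwise intervals.

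This needs SAP wording and one standard procedure on visit dates already held; no new data are required. The SAP change log shows version 2.0 was issued during the main analysis, so a later addition should be described as such in the study report. The downside is that medians become intervals and look less precise, though the precision given up was only apparent. Early endpoints barely change: for a true median of 4 days, Kaplan-Meier averages 4.3 to 4.4 and the interpolated interval-censored estimate 3.9 to 4.2.

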#### 4.7.2 Rasch-Built Linearly Weighted Overall Disability Scale (R-ODS)

The response options for each item of the Rasch-Built Linearly Weighted Overall Disability Scale (R-ODS) used for the efficacy endpoints will be assessed for all subjects as per the schedule of assessments. The final questionnaire comprises 24 items ranging from ability to read a book or newspaper (as the easiest item to accomplish) to ability to run (most difficult item to accomplish). The response options for each item are:

0 = Not possible

1 = Possible with effort

2 = Easy to perform

The obtained raw summed score is subsequently translated to a convenient centile metric ranging from 0 (most severe disability) to 100 (no disability at all), as described in [Appendix 2](#), which will be used for summary statistics and analyses. To note, the centile metric will be calculated only if all 24 items have data, otherwise this will be missing.

Summary statistics will be presented in tables for the actual values and absolute change from baseline by time point for the centile metric.

In addition, the number and percentages of subjects with an increase from baseline in R-ODS scale by at least 6 points on the centile metric score will be presented using descriptive statistics by time point.

Similarly, the number and percentages of subjects with all R-ODS items above 0 at week 26 will be presented.

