## 2.4 Data pre-processing

Difference between the value at each assessment and value at baseline for the efficacy parameters as an absolute change and percentage change will be calculated as:

$$\text{Absolute change at visit } x = \text{Value at visit } x - \text{value at baseline}.$$

$$\text{Change in \% at visit } x = \frac{\text{absolute change at visit } x}{\text{value at baseline}} \cdot 100.$$

The proportion of subjects with improvement since baseline at each visit will be calculated as:

$$\text{Proportion at visit } x = \frac{\text{number of subjects with improvement at visit } x}{\text{number of subjects at baseline}}.$$

Mean difference from baseline to each visit will be calculated as:

$$\text{Mean difference at visit } x = \frac{\text{sum of absolute change from baseline at visit } x}{\text{number of subjects at visit } x}.$$

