#### 4.1.2 Baseline definition

Baseline value is defined as the last non-missing assessment before the subjects start on the treatment. Change from baseline will be calculated as the difference between values for a given timepoint after baseline and baseline values (timepoint after baseline value minus baseline value). If the post-baseline value or baseline value are missing, then the change from baseline will also be missing.

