#### 4.1.3 Data imputation

In general, missing data will remain as missing and the missing values will not be imputed. There are some exceptions described below.

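### As the SAP is written, one blank R-ODS item at follow-up counts a subject as not improved, even when a 6-point gain is certain

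*SAP*

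**What the plan says.** - **Scoring.** SAP 4.7.2 converts the 24-item raw sum to a centile metric, with this condition: "To note, the centile metric will be calculated only if all 24 items have data, otherwise this will be missing".
- **Endpoints.** By time point, SAP 4.7.2 reports "the number and percentages of subjects with an increase from baseline in R-ODS scale by at least 6 points on the centile metric score". It adds that "the number and percentages of subjects with all R-ODS items above 0 at week 26 will be presented". It states no denominator for either endpoint and no rule for deciding responder status from a partly completed form.
- **Change from baseline.** SAP 4.1.2: "If the post-baseline value or baseline value are missing, then the change from baseline will also be missing".
- **Imputation.** SAP 4.1.3: "In general, missing data will remain as missing and the missing values will not be imputed". The exceptions set out there concern adverse event and medication dates.
- **Proportion formula.** SAP 2.4 opens its rule with "The proportion of subjects with improvement since baseline at each visit will be calculated as" and divides by the "number of subjects at baseline". The mean difference in the same section divides by the "number of subjects at visit".
- **Protocol.** Section 12.3.4.8 asks only for descriptive statistics by time point. Section 7.1.2 schedules the R-ODS at Screening and at seven later time points, so there is only one pre-dose assessment.

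**The concern.** Each rule is ordinary when read alone. Together they turn one unanswered question into a non-response. A subject with a full baseline and 23 of 24 follow-up answers has no centile, hence no change and no place in the numerator. The subject was present at baseline, so the denominator still includes them. The error runs one way: it can remove responders and never adds any.

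The loss is also largely avoidable. A single item is worth 0, 1 or 2 raw points, and the 6-point threshold is often passed or missed by far more than that.

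The study has one arm and no testing, so these descriptive proportions and their intervals are themselves the efficacy result. A downward shift passes directly into what is reported.

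**Working it through.** **Inputs.** 24 items scored 0 to 2 (SAP 4.7.2); the raw-to-centile table (SAP Appendix 2); a threshold of 6 centile points (SAP 4.7.2); about 30 subjects (SAP 2.2). The plan states no figure for this endpoint, so there is none to reproduce. The item-blank rate q is not in the documents and is assumed below.

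**Step 1: what one blank can change.** If the 23 answered items sum to t, the true raw sum lies between t and t + 2. In Appendix 2 that spread is worth 2 to 5 centile points for t from 2 to 41, and 7 to 12 points at the extremes (t of 0 or 1, and 42 to 46). A 6-point rise needs 1 to 5 raw points, depending on baseline.

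**Step 2: an example.** Baseline raw 4 is centile 16. At follow-up, 23 items sum to 40 and one is blank. The true raw sum is 40 to 42, which is centile 69 to 73. The gain is 69 − 16 = 53 to 73 − 16 = 57 points, so the subject is a responder whatever the blank was. SAP 2.4 counts the subject as not improved.

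**Step 3: how often one blank matters.** There are 49 baseline raw scores and 47 possible 23-item sums, so 49 × 47 = 2,303 pairs:
- 947 are certain responders (gain of at least 6 with the blank scored 0);
- 1,263 are certain non-responders (gain below 6 with the blank scored 2);
- 93 are uncertain, and 93/2,303 = 4.0%.

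The pairs are unweighted, so 4.0% describes the scale and is not a patient probability.

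**Step 4: cost per subject.** 1/30 = 3.3 percentage points. As an illustration, suppose 24 of 30 are true responders and 3 of the 24 have one blank at the visit, all three certain responders on the bounds:
- SAP as written: 21/30 = 70.0%
- dividing by subjects with a score: 21/27 = 77.8%
- counting certain responders: 24/30 = 80.0%

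**Step 5: expected size under assumed blank rates.** With independent blanks at the visit only, P(form complete) = (1 − q)^24, and a true 80% is reported on average as 0.80 × (1 − q)^24.

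| Assumed q | Forms incomplete | Expected out of 30 | True 80% reported as |
|---|---|---|---|
| 0.1% | 2.4% | 0.7 | 78.1% |
| 0.5% | 11.3% | 3.4 | 70.9% |
| 1% | 21.4% | 6.4 | 62.9% |
| 2% | 38.4% | 11.5 | 49.3% |

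**Step 6: does dropping undetermined subjects work?** Not for the week 26 endpoint. A form with a blank can be a certain failure (some observed 0) but never a certain success. Take a true 60% and q = 1%. Determined successes are 0.60 × 0.786 = 0.472. If essentially all failures are determined, they make up 0.40. The reported proportion is then 0.472/(0.472 + 0.40), about 54%. The denominator must therefore stay fixed.

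**The case against.** **The denominator is inferred.** The SAP 2.4 formula speaks of improvement, the R-ODS endpoint speaks of an increase, SAP 4.7.2 names no denominator, and output shells not seen here could use another. This stands as a caveat. However, SAP 2.4 is written for the efficacy parameters and exempts no scale, so on the text available it governs. If a shell differs, the two need reconciling.

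**The all-24-items rule is legitimate.** The Appendix 2 table converts a full raw sum, and the MRC sum score follows the same principle. This stands. Under independent blanks that rule alone causes no bias: dividing by subjects with a score returns 80% in expectation. The bias arises when the SAP 2.4 denominator acts on it.

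**The size is speculative.** No blank rate is given. At the same blank rate, clustered blanks would spoil fewer forms, and data cleaning may keep blanks rare. This stands; the table is a range of assumptions, not a forecast.

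**The consequence is limited.** There is no testing, and data are listed by subject and time point, so gaps would be visible. This stands in part: a listing shows the gap but does not correct the reported proportion.

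A reader might infer two stronger points that the documents do not support:
- **Blanks at baseline too.** If these also count against the subject, the exponent becomes 48, and a true 80% would read as 63%, 49% or 30% at 0.5%, 1% or 2%. That requires a subject without a baseline score to remain among the subjects at baseline. The phrase can equally mean subjects with a baseline value; they then leave both counts, and the figures return to 71%, 63% and 49%.
- **Worse bias in the acute phase.** No passage says that bed-bound or ventilated patients leave single items blank. The scale has a code, 0, for activities that are not possible. A patient who cannot respond at all yields a wholly missing form, which is a different problem.

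**Conclusion.** The point holds for a blank item at follow-up in a subject with a complete baseline. SAP 2.4, 4.1.2, 4.1.3 and 4.7.2 together count that subject as not improved, including when the 6-point gain is certain. The direction is always towards fewer responders, at about 3.3 percentage points per responder lost if N is 30. The expected total depends on an item-blank rate that the documents do not give: from zero with complete forms to a true 80% read as about 49% at an assumed 2%, with independent blanks at the visit only. This is bias in a descriptive proportion and its interval, not an error-rate problem. The week 26 endpoint also lacks a blank-item rule. The change is worth making because it is cheap and most one-blank combinations in Appendix 2 leave no doubt about the 6-point classification.

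**What to change.** Amend SAP 4.7.2 as follows.

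1. **6-point endpoint only.** Count a subject as a responder if the gain is at least 6 with blank visit items scored 0 and blank baseline items scored 2. Count a non-responder if the gain is below 6 with blank visit items scored 2 and blank baseline items scored 0. Otherwise the subject is undetermined.
2. **Denominator.** State a fixed full analysis set denominator. Deaths and wholly missing visits count as not improved, as SAP 2.4 implies. Limiting the denominator to determined subjects would drop them and could bias the proportion upward.
3. **Reporting.** At each visit show the number undetermined, and give the proportion twice: with undetermined subjects as non-responders, then as responders.
4. **Week 26 endpoint.** Use the same fixed denominator. Any observed 0 is a failure. Forms with blanks and no observed 0 are undetermined, reported with the same lower and upper proportions and not removed.
5. **Centile summaries.** These can keep the all-24-items rule.

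The cost is a few sentences and one extra derivation from item data already collected. A few subjects will remain undetermined, so some visits will show a narrow range in place of a single figure.
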